### 3. Research Procedures

Provide a detailed chronological description of all research procedures.

A screening log of all potential subjects will be kept at our site. All screening evaluations must be reviewed by the investigator to establish patient eligibility prior to registering the patient for this study.

The following screening evaluation should be completed for all subjects on the first visit:

- Informed consent and photograph release form
- Focused medical history including diagnosis of lesion if applicable. This includes general questioning about the patient's health, well-being, allergies, and medications, and history of the skin lesion in question as identified by the patient and confirmed by the physician.
- Focused skin exam. This includes a detailed medical examination of the skin lesion in question.
- Documentation of area of skin to be studied. This will be determined by the patient's indication and confirmed by the physician.

On visit number one of the study, patients will consent to the study, and an area of skin to be studied will be photographed by digital photography. If the study area is on the face, subjects will be offered to protect their identity.

Non-invasive imaging will then be performed with OCT. Each individual scan with OCT takes about 30 seconds to complete, and we may perform multiple scans on larger lesions. Based on the data and information obtained, the appropriate laser device and settings will be applied for the most optimal treatment to achieve the best results with the fewest side effects. Then laser treatment will be performed on the lesion of interest. Immediate post-treatment imaging and photography will be conducted to assess the results of the treatment. This first visit should take no more than 1.5 hours: approximately 20 minutes for a medical history and focused skin examination, 30 minutes for imaging including photographs, and 30 minutes for laser treatment. These times are all maximums and will likely be shorter. The patient may take as long as needed to consent and is permitted to take the consent form home and return another day to sign and enroll.

Some subjects may be asked to participate in more than one imaging session. They will have the option of refusing participation in additional sessions. Follow-up examinations will be performed every 4 weeks. During these examinations, photography and imaging of the lesion of interest will be performed with optional laser treatments to be performed at the discretion of the treating physician and the patient. If no laser treatment is necessary, then the visit should take no more than 30 minutes for a quick follow-up and imaging. Additional laser treatment will require no more than 30 minutes to complete. The number of follow-ups is also determined at the discretion of the treating physician and the patient but could range from 1 to 6 depending on the response of the lesion to treatment.

Matched prospective controls will be gathered to be compared against the imaged, treated, experimental group. The prospective controls will be matched to age, gender, skin type, and type of skin lesion. They will be gathered via a retrospective chart review by abstracting and data directly from our own records.

Describe the duration of a subject's participation in the study. If there are sub-studies, include duration of participation in each sub-study.

For each visit: history and skin examination-30 minutes, imaging – up to 30 mins, and laser treatment – up to 30 mins. These are all maximums and will likely be shorter.

At a follow-up, the patient may or may not receive a laser treatment thus shortening the visit. A patient would be expected to have 1-6 follow ups depending on their response to treatment, so their maximum time in this study could range from about 1 to 6 months. Each follow-up visit is made about 4 weeks from the prior visit.

List data collection instruments (e.g., measures, questionnaires, interview questions, observational tool, etc.).

*Investigator-authored, non-standardized, or un-validated measures must be submitted for review.*

Standardized photography,  
OCT

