**NON-TECHNICAL SUMMARY**

Provide a brief non-technical summary or synopsis of the study that can be understood by IRB members with varied research backgrounds, including non-scientists and non-affiliated members.
The purpose of this study is to obtain information (such as lesion depth, depth of the most superficial part of the lesion, and the size and density of blood vessels) with the assistance of an imaging device, and use this information to assist in selection of laser settings for the treatment of skin conditions. The imaging modality is called Optical Coherence Tomography (OCT). Multiple laser modalities will be used including intense pulsed light (BroadBand Light, Profractional Sciton), pulsed dye laser (Vbeam Perfecta, Candela), long-pulse 755nm (GentleLASE, Candela), Sciton long-pulse 1064nm lasers, and non-ablative and ablative fractional resurfacing (Profractional, Sciton) lasers. All of the lasers noted above are the only ones that will be used in this study; they have 510k clearance and are being used as per their approved indications in this study. The choice of laser type is based on the skin lesion and is recommended by the physician, and subjects who are going to enroll in this study will already be planned to undergo laser treatment as a standard of care for their condition. This is a pilot study that will explore the utility of skin imaging in guiding the laser treatment of skin lesions.

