### **2. Study Design**

Include an explanation of the study design (e.g., randomized placebo-controlled, cross-over, cross-sectional, longitudinal, etc.) and, if appropriate, describe stratification/ randomization/blinding scheme.

This is a longitudinal study with matched prospective controls. The patients will undergo treatment and follow-up over the course of 1-7 months. Their results will be compared to that of matched prospective controls with similar treatment and follow duration. There is no placebo, and patients will not be blinded.

Patients will be stratified based on their lesion type and the size of the lesion as these factors may impact the response to laser treatment and thus the data measurements from OCT. Photographs of the patients' treated lesions will be rated for lesion improvement by blinded physicians. OCT measurements of the lesion of interest will be used to validate the improvement and cosmetic results.

Provide precise definitions of the study endpoints and criteria for evaluation; if the primary outcomes are derived from several measurements (i.e., composite variables) or if endpoints are based composite variables, then describe precisely how the composite variables are derived.

Primary endpoints include photographic improvement of the lesion(s) of interest after 1 or more laser treatments. Two board certified dermatologists grade the degree of improvement (clearance of the lesion) in quartiles (no clearance=0-25, mild clearance=26-50, good clearance=51-75, excellent clearance=76-95, complete clearance=96-100). It will be up to the experienced treating dermatologist to determine the number of treatments necessary for maximum clearance of the lesion(s).

Secondary endpoints include measurements with OCT, which show reduced lesion thickness, lesion size, size of blood vessels, and density of blood vessels, and number of superficial blood vessels.

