**How Obtained: Indicate all that apply:**

The study team will request specific patient information/data from UCIMC Health Information Management Services.

The study team will review their patients' records and abstract data directly from those records.

The study team will request specific patient information/data from UCI Health Honest Broker Services. Describe the following:

Cohort selection criteria (e.g., use the available Clinical Terms from the Cohort Discovery Tool such as Demographics: Gender, Diagnoses: Asthma, Procedures: Operations on digestive system): <Type here>

Expected cohort size/patient count: <Type here>

Cohort attributes or data elements (e.g., lab test values, medication, etc.): <Type here>

Other; explain: <Type here>

For studies that involve use of existing (i.e. on the shelf; currently available) clinical data, specify the time frame of the clinical data to be accessed (e.g. records from January 2002 to initial IRB approval).

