##### Statistical Analysis Plan

Primary Objective: The outcome of degree of improvement will be compared between those previous patients that were treated conventionally as a prospective control and those prospective patients who will be treated with assistance from the OCT device. We will use a two-sample t-test to examine the difference in degree of improvement between the two groups at each treatment.

Secondary Objective: We will present the mean/standard deviation and 95% confidence interval of all secondary outcomes (including lesion thickness, size, size of blood vessels, and density of blood vessels, and number of superficial blood vessels.) at each treatment.

2. Describe the primary statistical method(s) that will be used to analyze the primary outcome(s) or endpoints.

N/A

3. Describe the secondary statistical method(s) that will be used to analyze the secondary outcome(s) or endpoints.

N/A

4. If appropriate describe secondary or post hoc analyses of primary outcome(s) or other exploratory analysis.

N/A

5. Sample Size Determination: Explain how the overall target sample size was determined (e.g., power analysis; precision estimation), providing justification of the effect size for the primary outcome based on preliminary data, current knowledge/literature and/or cost consideration; if appropriate, provide sample size justification for secondary outcomes. Power analysis should (at least) match the primary outcome/endpoint.

Literature indicated that laser treatment of skin lesions yields varying degree of clearance across different types of lesions. For example, the Ashinoff et al. 1991 study showed 50% lesion clearance after 3 laser treatments for port wine birthmarks in 12 infants. Another Ashinoff et al. 1991 study showed 70% lesion clearance after 3 laser treatments for capillary hemangiomas in 10 infants. The Clark et al. 2002 study showed 50% lesion clearance after 3 laser treatments for rosacea in 12 adults. Last but not least, the Geronemus 1991 study showed 90% lesion clearance after 1 laser treatment for spider telangiectases in 12 adults. Based on these data, we calculated a mean of 65% ( $\pm 20\%$ ) lesion clearance after 3 laser treatments for any lesion type. Adjusting for the unique characteristics of our patient population at UCI, we estimated a mean lesion clearance of 40% ( $\pm 20\%$ ) after 1 laser treatment for any lesion type.

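### Chart-review controls are not restricted by treatment period or treating dermatologist, and comparable treatment is left undefined, so differences in these would be counted as an OCT effect

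*Combined protocol and SAP*

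**What the plan says.** Section 6, Research Procedures, states how controls are chosen: "The prospective controls will be matched to age, gender, skin type, and type of skin lesion". The next sentence gives their source: "They will be gathered via a retrospective chart review by abstracting and data directly from our own records". The primary objective in the Statistical Analysis Plan describes them as "those previous patients that were treated conventionally as a prospective control" and compares the groups by a two-sample t-test, with no covariates and no use of the matching.

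Study Design adds two things. The comparison is with "matched prospective controls with similar treatment and follow duration", and "Patients will be stratified based on their lesion type and the size of the lesion". Neither addition is repeated in the matching rule.

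On equipment, the Non-Technical Summary says "Multiple laser modalities will be used including intense pulsed light", then names the devices and adds: "All of the lasers noted above are the only ones that will be used in this study". It attributes the choice of laser type to the lesion and the physician. Research Procedures instead has the device and settings follow from the OCT data.

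The items to be screened for controls (Section 3, Screening and Determining Eligibility) are age, diagnosis, lesion location, and clearance and response. Device, dermatologist and treatment date are not among them.

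**The concern.** The study group is treated from now on, and the controls, on the Statistical Analysis Plan's own description, were treated earlier. A difference in period is therefore built in, and no limit is set on its length. The dermatologist who gave the treatment is not a matching or stratification factor either. Clearance can depend on who operates the laser, which device was available, and how practice stood at the time. The t-test attributes the whole difference between group means to OCT guidance. Matching on patient and lesion traits cannot remove an operator or period difference. Blinded rating of photographs protects the grading but does not make the treatments comparable. If device, operator and date are not recorded, the imbalance cannot even be seen afterwards.

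**Working it through.** **Inputs.** From the sample-size paragraphs of Statistical Considerations: clearance of 60% with OCT against 40% without, a difference of 20 points; ±20%, read here as the SD; 17 per group; two-sided 5% two-sample t-test; 80% power. The enrolment table in Section 3 allows up to 30 per group. The bias *b* is an assumption, because the documents give no operator, period or device effect.

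**The plan's own figure.**
- SE of the difference = 20 × √(2/17) = 6.86 points, with 32 degrees of freedom.
- Noncentrality at 20 points = 20/6.86 = 2.92.
- Exact (noncentral t) power at 17 per group = 80.7%. The exact requirement is 16.7 per group, so 17. The stated sample size reproduces.
- The smallest observed difference that reaches significance = 2.037 × 6.86 = 14.0 points.

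**No OCT effect, net bias *b*.** Noncentrality = *b*/6.86. For 30 per group, SE = 20 × √(2/30) = 5.16 with 58 degrees of freedom.

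| Assumed *b* (points) | Noncentrality (17 per group) | Two-sided rejection, 17 per group | Two-sided rejection, 30 per group |
|---|---|---|---|
| 0 | 0 | 5.0% | 5.0% |
| 2.5 | 0.36 | 6.4% | 7.6% |
| 5 | 0.73 | 10.9% | 15.9% |
| 10 | 1.46 | 29.3% | 47.8% |

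A larger sample makes the false-positive rate worse, because the bias stays fixed while the SE shrinks.

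**True OCT effect of 20 points, bias against the study group.** A 5-point bias leaves a net difference of 15 points and power of 56.4%. A 10-point bias leaves 10 points and power of 29.3%.

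**Which differences are bias.**
- *Period:* not matched, not stratified and not bounded in the visible text, so all of it is bias.
- *Dermatologist:* not matched and not stratified, so all of it is bias.
- *Laser:* if OCT leads the physician to another device, as Research Procedures allows, that difference is part of the effect under study. Only laser differences with another cause, such as equipment available in earlier years or operator habit, are bias.

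**The case against.** Several points on the other side have force.

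- **The plan does ask for similar treatment.** The Study Design phrase can be read as similar treatment together with similar follow-up duration, and lesion size is a stratification factor. A reader might infer that controls are matched on nothing beyond the four listed traits; that goes too far. What stands is that the phrase is undefined, is absent from the operative rule, and on any reading does not fix the operator or the year.
- **The closed laser list may cover controls.** The enrolment table makes the control group part of the study, so the list can be read that way. The sentence looks forward, however, and does not say that past charts must involve those devices.
- **The team's own records may mean its own patients.** That would partly fix the operator. It is plausible but not stated.
- **The missing time frame is weak evidence.** The form's prompt, "specify the time frame of the clinical data to be accessed (e.g. records from January 2002 to initial IRB approval", has no visible answer. A reader might infer that no period was set. The form's answers and tick marks are largely lost in the public text, a separate abstraction sheet is called for that is not in these documents, and treatment dates are ticked as collected in Section 11. The point therefore rests on the matching rule and the analysis, not on this blank.
- **Prospective controls would change the picture.** Sections 1 and 3, Study Design and the sample-size paragraph all call the controls prospective. If they are concurrent, the period argument falls away. The documents contradict themselves here, and the operator question remains either way.
- **It is a pilot, and no bias has been shown.** Both are true. The plan nevertheless makes a powered two-sided 5% comparison, and its rules would neither prevent nor reveal such a bias.

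**Conclusion.** The concern holds for treatment period and treating dermatologist, and for laser differences that OCT did not cause. As written, the plan lets these enter the primary comparison, and an unadjusted t-test cannot separate them from OCT guidance.

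A reader might infer that every difference in laser between the groups is a bias. The documents do not support that, because Research Procedures makes device choice partly a consequence of OCT. Nor do they show that a bias exists, which way it runs or how large it is. The rejection rates of about 11% and 29% are conditional on an assumed net bias of 5 or 10 points (a quarter or a half of the planned effect), no OCT effect, SD 20 and 17 per group. They show how sensitive the test is, not what will happen. The matter should be settled before charts are pulled.

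**What to change.** 1. Reconcile the label prospective with the retrospective chart review, so that one description of the controls holds throughout.
2. If chart controls are kept, add to the matching rule in Research Procedures that a chart qualifies only if the first treatment was given (a) by a dermatologist who also treats the study group, (b) with a laser on the Non-Technical Summary list, and (c) within a stated recent window ending at the first OCT enrolment. The sponsor should set the window's length by chart availability and enter it under the time-frame item of the existing-data section. Take the most recent eligible matches first. This also gives similar treatment a definition.
3. Record device, dermatologist and treatment date in both groups and tabulate them by group.
4. Do not match device one to one. Reconcile the Non-Technical Summary with Research Procedures on how the laser is chosen, and state whether that choice is part of the OCT strategy.

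The cost is protocol wording, up to three abstraction fields (treatment dates may already be collected) and a smaller pool of eligible charts. With four matching factors at one site, the sponsor should check that 17 matches can still be found. No extra patients are needed. If truly concurrent controls are intended, the protocol should say that the same dermatologists treat them with the same lasers over the same period. Allocating them by chance would be a redesign, not a wording change.

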**Originally collected for research purposes:**

NO – Please explain: [<Type here>](#)

YES – UCI IRB approval granted under IRB protocol number (i.e. HS#): [<Type here>](#)

YES – Non-UCI IRB approval granted. Confirm one of the following:

A copy of the IRB Approval Notice and Consent Form for the original research collection will be submitted with the IRB application (APP). The IRB Approved Consent Form does not preclude the proposed activity.

A copy of the commercial Vendor Policy or a Letter from the Vendor attesting that the information was collected and will be shared in an appropriate and ethical manner will be submitted with the APP. The vendor's policy does not preclude the proposed activity.

5. Provide a complete list of the **data points, variables, and/or information** that will be collected **during the screening process** (i.e. data abstraction form). *Note: Only the minimum information necessary to determine subject eligibility should be collected during the screening process.*

For the experimental group, we would screen for the patient's age, type of lesion/diagnosis, location of the lesion, and the patient's willingness and ability to participate in the study.

For the control group, we would screen for the patient's age, type of lesion/diagnosis, location of the lesion, and the clearance of the lesion and response to treatment.

Check here if the list is submitted as a separate document with the application.

6. Specify what will happen to the information and/or biospecimens, if the potential subject is not eligible to participate in the study. *Note: Information or biospecimens of non-eligible subjects, may not be included as part of data analysis or disclosed beyond the study.*

The study team plans to destroy the identifiable information and/or biospecimens at the earliest opportunity consistent with conduct of the research. Describe the protocol specific plan and timeframe for destruction: [<Type here>](#)

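### Controls can be selected with their outcome in view, and lesion size, named as affecting response, enters neither the matching nor the primary test

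*Combined protocol and SAP*

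**What the plan says.** All references are to the combined protocol and SAP.

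- **Matching (Section 6, 3. Research Procedures).** Controls are to be "matched to age, gender, skin type, and type of skin lesion". The same paragraph says they are obtained by retrospective review of the team's own charts.
- **Control screening items (Section 3A, item 5).** The list for controls gives age and diagnosis, followed by "location of the lesion, and the clearance of the lesion and response to treatment". Gender, skin type and lesion size do not appear. The form limits this list: "Only the minimum information necessary to determine subject eligibility should be collected during the screening process".
- **Eligibility (Section 3, Eligibility Criteria).** The criteria concern ability to follow instructions, age (all ages) and being scheduled for laser treatment of a lesion. Clearance is not among them.
- **Stratification (Section 6, 2. Study Design).** Patients are to be "stratified based on their lesion type and the size of the lesion as these factors may impact the response". Photographs are to be rated by blinded physicians.
- **Primary analysis (Section 6, 5. Statistical Considerations).** Improvement in previously treated controls is compared with improvement in OCT-assisted patients by a two-sample t-test at each treatment. No stratum or covariate is named.
- **Status of the controls.** The enrolment table, Study Design and the sample size paragraph call the controls prospective. Research Procedures and the Statistical Analysis Plan point to past patients and existing charts.

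**The concern.** The comparison is not randomised, so its credibility depends heavily on how controls are picked. Two weaknesses bear on that.

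First, a control taken from past charts already has an outcome. If the person screening charts records clearance while deciding who enters, the choice among otherwise suitable candidates can follow the outcome, deliberately or not. Picking poorer responders would flatter OCT guidance; picking well-documented good responders would hide a benefit.

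Second, the protocol itself says lesion size may affect response. If the OCT group happens to have smaller or larger lesions than the controls, the primary test attributes the difference to OCT.

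**Working it through.** **Step 1. Compare the lists.**

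| Item | Matching variable | On control screening list | Stratification factor | In primary test |
|---|---|---|---|---|
| Age | yes | yes | no | no |
| Lesion type | yes | yes | yes | no |
| Gender | yes | no | no | no |
| Skin type | yes | no | no | no |
| Lesion size | no | no | yes | no |
| Clearance/response | no | yes | no | outcome |

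The control list has an outcome item and lacks a baseline factor that the protocol says matters. The step at which controls are chosen is the step at which clearance is seen, and no sentence says a control is fixed first.

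**Step 2. Reproduce the plan's sample size.** Inputs from Sample Size Determination: 60% versus 40% clearance, SD 20 points, two-sided 5%, 80% power.

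- Standardised difference: (60 − 40)/20 = 1.0.
- Normal approximation: n = 2 × (1.960 + 0.842)² / 1.0² = 15.7, so 16 per group.
- Exact noncentral t: 16.71, so 17 per group, with power 80.7%.

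The stated 17 per group is reproduced. It assumes no bias in the group difference.

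**Step 3. Effect of a bias on the test.** The documents give neither a size effect nor a measure of outcome-aware selection, so the bias *b* is an assumption. With no true effect, the t statistic has 32 degrees of freedom and noncentrality (b/20) × √(17/2) = (b/20) × 2.915. The false-positive rate is the probability that it falls beyond ±2.037. If the bias runs against OCT and the true effect is 20 points, the noncentrality is ((20 − b)/20) × 2.915.

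| Assumed bias (points) | Noncentrality, no true effect | False-positive rate | Power if bias is against OCT |
|---|---|---|---|
| 0 | 0 | 5% | 80.7% |
| 2 | 0.292 | 5.9% | 72.1% |
| 4 | 0.583 | 8.7% | 61.9% |
| 5 | 0.729 | 10.9% | 56.4% |
| 6 | 0.875 | 13.6% | 50.8% |
| 8 | 1.166 | 20.5% | 39.6% |
| 10 | 1.458 | 29.3% | 29.3% |

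**Step 4. What size imbalance alone would need.** Bias from size is roughly the difference between groups in the share of large lesions, times the clearance difference between large and small lesions. If that clearance difference were 20 points (an assumption), share differences of 0.1, 0.2 and 0.3 give biases of 2, 4 and 6 points. Reaching 5, 8 or 10 points would need share differences of 5/20 = 0.25, 8/20 = 0.40 or 10/20 = 0.50. The upper rows therefore need a marked imbalance, a stronger size effect, or outcome-aware selection on top.

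**The case against.** A reader might infer that the match cannot be made, because gender and skin type are missing from the control list. The documents do not support that. The list covers eligibility screening only, and the OCT-group list has the same gaps: "For the experimental group, we would screen for the patient's age, type of lesion/diagnosis, location of the lesion, and the patient's willingness and ability" to take part. Gender and skin type could be taken later from the same charts. The form calls for a separate abstraction sheet or case report form for existing records (Section 6, Use of Existing Information/Data). That sheet was not available for this review, nor can the box for a separately submitted list be read. What stands is narrower: the documents do not show these items, or baseline size, being abstracted for controls.

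A reader might also infer that lesion size is wholly uncontrolled, or that matching is the only safeguard. Study Design does name size for stratification. The gap is that this intention reaches neither control selection nor the test.

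The strongest objection concerns the status of the controls. If they are truly enrolled prospectively, their clearance is unknown at entry and the selection concern falls away. But Research Procedures and the Statistical Analysis Plan describe past patients, and listing clearance as a screening item makes sense only on that reading. The conflict has to be reconciled either way, and the point about size remains.

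Finally, no rule tells staff to select on clearance, and the endpoint is graded from photographs by blinded physicians rather than read from the chart. That limits rating bias. It cannot repair a control group already selected with knowledge of outcome.

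The 50% to 90% clearance range in the sample size paragraph should not be used to size this problem: it concerns lesion type, which is matched, and mixes results after one and three treatments.

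**Conclusion.** The point holds in two parts. On the chart-review reading, the text allows controls to be selected with their outcome known. On either reading, lesion size is named as relevant to response but is not carried into the matching or the unadjusted t-test. The absence of gender and skin type from the screening list is a lesser matter of missing detail.

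The size of any bias is unknown. With 17 per group, SD 20 points and normally distributed clearance, an assumed bias of 5 to 10 points takes the two-sided false-positive rate from 5% to between 10.9% and 29.3%; 2 points takes it only to 5.9%. A bias of 10 points is half the 20-point effect the study is powered to detect. These figures show sensitivity and do not estimate what will happen. The documents do not show that outcome-based selection is intended. The text should be changed before any control is chosen, since the problem cannot be reliably undone afterwards.

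**What to change.** 1. **Section 3A, item 5.** Take clearance and response out of control screening. List gender, skin type and baseline lesion size with age, diagnosis and location as the items used for selection. State that control outcomes are collected at a later step: abstraction of outcome data and blinded photograph grading after selection is complete.
2. **Section 6, Research Procedures.** Add baseline lesion size, in a small number of bands set in advance, to the matching variables. Alternatively, keep the present matching variables and carry the lesion type and size strata from Study Design into the primary analysis, for example as terms in a linear model in place of the unadjusted t-test.
3. **Same section.** State that each control is fixed on baseline data, and the choice recorded, before its outcome notes or photographs are opened.
4. **Throughout.** Reconcile the descriptions of the controls as prospective and as drawn from past charts.

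The cost is a few sentences and a revised abstraction sheet; the added items should be available from the charts or baseline photographs. Matching on size will leave somewhat fewer eligible controls, so age bands may need to be wide. Adjusting instead uses a few degrees of freedom from 34 patients, so the strata should be kept few.
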